Secondary performance outcomes include the feasibility of inducing, maintaining, and rewarming patients from targeted temperature management using the Esophageal Cooling Device. Specifically, cooling rate, rewarming rate, and the percent of time during the goal-temperature maintenance period within 1°C of goal temperature (typically 33°C, but with some centers using anywhere from 32°C to 36°C) will be measured.

Secondary safety outcomes include evaluation of adverse events including the following: cardiac arrhythmias, severe bradycardia, myocardial infarction/re-infarction, dysphagia, odynophagia, aspiration pneumonia, non-aspiration pneumonia, reflux, esophageal injury, and esophagitis.

Specific definitions of adverse events and the methods used to identify and diagnose each during the treatment and 30-day follow-up phases are as follows:

- Cardiac arrhythmias - recording of atrial or ventricular arrhythmias during course of treatment.
- Severe bradycardia - heart rate < 30/min and necessitating pacing and cessation of TH.
- Myocardial infarction - universal definition of myocardial infarction as per the joint ESC/ACCF/AHA/WHF Task Force for the Redefinition of Myocardial Infarction.[50]
- Dysphagia - report from patient of difficulty in swallowing for more than 24 hours after cessation of device use, diagnosed with a Modified Barium Swallow Study, Videofluoroscopic Swallow Study, or patient self-report.
- Odynophagia - report from patient of pain with swallowing for more than 24 hours after cessation of device use, diagnosed by subjective patient sensation.
- Aspiration pneumonia - demonstration by chest X-ray of evidence of aspiration pneumonia, as diagnosed by treating physician, within 24 hours of cessation of device use.

- Non-aspiration pneumonia - demonstration by chest X-ray of evidence of pneumonia within 24 hours of cessation of device use that is diagnosed by the treating physician as non-aspiration pneumonia.
- Reflux - report of symptoms from patient within 3 days of recovery, with diagnosis via esophageal pH monitoring or endoscopy.
- Esophageal injury - evidence of traumatic and/or ischemic esophageal injuries diagnosed by gastroenterologist evaluation via esophagogastroduodenoscopy as warranted or indicated, and describing the absence of necrosis or not according to the Zargar classification used for caustic injuries within 3 days of recovery .

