Written informed consent will be obtained from each patient's next of kin or patient's legal representative before inclusion. Surviving patients without severe neurological sequels will give their written informed consent. When a patient has recovered, and is able to do so, he/she has to sign the informed consent form personally.

This study will be conducted according to the principles of the Declaration of Helsinki (as amended October 2013) of the World Medical Association. The protocol will be submitted and approved by the local Ethics Committee of the institution.

Randomization:

Randomization: none

Esophageal Cooling Device:

The placement of the Esophageal Cooling Device will follow standard recommendations as per Instructions for Use. The Esophageal Cooling Device will be connected to the appropriate console (Meditherm III, Blanketrol II, or Blanketrol III).

Other treatments:

Standard treatments for traumatic brain injury will follow local guidelines. Fluid and other management is left at the discretion of the attending physician.

Data collection:

All clinical and biological parameters will be recorded according to the Utstein-style recommendations for reporting resuscitation outcomes.[51] Neurologic outcome will be assessed according to the Cerebral Performance Category (CPC) score.[52] Initial temperatures will be measured via a tympanic or naso-pharyngeal temperature sensors in the prehospital field if available, or by other means used as standard of care. Continuous temperature measurement (specifically during cooling, maintenance, and rewarming) will be measured by bladder temperature sensors or rectal temperature sensors, and arterial temperature monitoring if available. Time of ECD placement in a patient will be recorded; the potential side effects (see above) will be recorded throughout the entire study..

Study assessments and procedures

Screening on Day 1

This visit includes the primary diagnostic procedures and the verification of the eligibility criteria. Subjects are eligible for the study will undergo the following procedures at this visit:

- Written informed consent (the form will be signed by a patients or legally acceptable representative);
- Previous medical history and co-morbidities;
- Physical examination including body weight, height and BMI, general appearance, heart, lungs, abdomen and extremities examinations;
- Demographics;
- Smoking habits;
- Alcohol consumption;
- Inclusion/exclusion criteria;

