- Concomitant medications;
- Pre-hospital data: scene of injury (place of residence/public place/other), witness injury (yes/no), time from emergency call to arrival of EMS personnel, estimated time from injury to basic life support, estimated time from injury to advanced life support, location patient intubated (on scene/in ambulance/in emergency department);
- First recorded temperature and method of temperature measurement;
- Glasgow Coma Score;
- Presence of pupillary and corneal reflex;
- Any sign of spontaneous breathing/agonal breathing/gasping at admission;
- Blood gas and FiO₂ (pO₂, pCO₂, BE, pH, lactate);
- Blood glucose;
- Troponin; (if obtained)
- BNP; (if obtained)
- ECG (normal/STEMI/LBBB/other);
- Echocardiogram (EF-normal, EF-moderately impaired, EF-severely); (if obtained)
- Head CT scan (at least the type of injury (subdural, epidural, subarachnoid, etc.) and relevant parameters for each (size, midline shift, volume of hematoma, etc.) should be recorded)
- Surgical interventions (if any)

After screening, subjects eligible for the study participation will undergo the following procedures during this time period:

- Temperature will be measured every hour from time point “0” to 39 hours. Time point “0” is the time either the patient or patient's legal representative, or close relatives signs the consent form. Method of temperature measurement should be recorded for each measurement. Two methods should be used for each time point measurement: 1) standard monitored route (rectal, Foley, intravascular, etc.); 2) temperature reported from the Blanketrol II
- Blood glucose and dose of insulin: 0 hr, 4 hr, 16 hr, 28 hr, 36 hr;
- Lowest and highest heart rate: 0 hr, 4hr, 16 hr, 28 hr, 36 hr;
- Lowest and highest mean arterial pressure: 0 hr, 4hr, 16 hr, 28 hr, 36 hr; (if arterial pressure is measured)

- Dose of vasopressor or other inotropic medication: 0 hr, 4hr, 16 hr, 28 hr, 36 hr;
- PaO₂, FiO₂ and mean airway pressure (MAP): 0 hr, 4hr, 16 hr, 28 hr, 36 hr;;
- Anti-shivering therapy administered, type and dose: 0 hr, 4hr, 16 hr, 28 hr, 36 hr;
- Central venous or mixed venous oxygen saturation: 0 hr, 4hr, 16 hr, 28 hr, 36 hr; (if measured)
- Arterial or venous lactate concentration: 0 hr, 4hr, 16 hr, 28 hr, 36 hr; (if measured)
- Blood gases (pH, pCO₂, pO₂, BE): 0 hr, 4hr, 16 hr, 28 hr, 36 hr; (if obtained as part of routine care)

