current standard (cooling blankets or evaporative cooling). For the endpoint of percent of time over the study period within 1°C of goal temperature (33°C), the treatment effect of the active control is large, since non-treatment results in essentially no attainment of goal temperature. An estimate of effect of the active comparator (M_1) is therefore greater than would be acceptable to use as a base for a non-inferiority margin. Consequently, a more restrictive non-inferiority margin (M_2) is then proposed of 15% (i.e., if the standard maintains goal temperature $+\/-1^\circ\text{C}$ for 60% of the time, and the ECD maintains goal temperature $+\/-1^\circ\text{C}$ for 85% of the time, the lower bound of the 95% CI on the difference between percent time at goal temperature between standard and test device is greater than 70%). Setting the type I error rate to 5%, for an alpha of 0.05, and a power of 80%, for a beta of 0.2, yields a sample size estimate of 15 patients in the study (with another at least 15 patients coming from historical controls with available esophagogastroduodenoscopy evaluation).

Data analysis: as recommended by current FDA guidance documents, both per-protocol (as-treated) and intent-to-treat analyses will be performed.[53] Lower 95% confidence limit for difference between groups must exclude the non-inferiority margins for primary end point in both efficacy and safety.

Abbreviation

ACT - Advanced Cooling Therapy

AE – adverse event

BNP - brain natriuretic peptide

ECG - electrocardiogram

GCS – Glasgow Coma Score

CPC - Cerebral Performance Category

CT – computed tomography

ECD - Esophageal Cooling Device

ECLS - Extra-Corporeal Life Support

EEG – electroencephalogram

LBBB - left bundle branch block

MAP – mean airway pressure

MRI - Magnetic Resonance Imaging

Protocol No ACT TBI-01

Version No 2.0 dated on 08-Dec-2014

OTC – over-the-counter

ROSC - Return of Spontaneous Circulation

SAE – Serious Adverse Event

SAPS – Simplified Acute Physiology Score

SOFA – Sequential Organ Failure Assessment

SSEP - Somatosensory evoked potentials

STEMI - ST-elevated myocardial infarction

TH - Therapeutic Hypothermia

References:

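### Percent time at goal has two conflicting definitions (a goal of 32 to 36°C over maintenance, or 33°C over the study period), and the prescribed goal is not listed for recording

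*Combined protocol and SAP*

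**What the plan says.** The endpoint appears in two places in the combined protocol and SAP.

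- **Secondary outcomes** defines it as "the percent of time during the goal-temperature maintenance period within 1°C of goal temperature". The goal is not one value: "typically 33°C, but with some centers using anywhere from 32°C to 36°C". The abstract also ties the measure to the maintenance period.
- **Statistical analysis** describes it as "percent of time over the study period within 1°C of goal temperature" and gives 33°C in brackets as that goal. The same paragraph proposes "a more restrictive non-inferiority margin" of 15%, illustrated by 60% of time at goal for the standard and 85% for the device, and arrives at 15 device patients with at least 15 historical controls.

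The recording lists (Data collection; Study assessments and procedures) are detailed. Temperature is taken hourly from 0 to 39 hours by two routes. "Method of temperature measurement should be recorded for each measurement". The second route is "2) temperature reported from the Blanketrol II", which is a reported temperature and is not described as a set-point. Placement time, insulin and anti-shivering therapy are also listed. The lists do not include the prescribed goal, the time it was set, any change to it, or the start and end of maintenance. No section says which goal is used for scoring if it changes. There is no randomization, and the comparison is with historical controls.

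**The concern.** Whoever computes this endpoint has to choose a goal and a time window, and the two sections give different instructions for both. Each choice carries its own error.

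- **33°C for everyone.** A patient whose clinician intended 35 or 36°C, and whom the device held there, scores close to zero. The endpoint then measures the prescribing choice as well as device performance.
- **The patient's own goal.** This fits the purpose of the endpoint, but only if the goal is on record before the temperatures are known. Otherwise it can be assigned, or moved, after the temperature curve has been seen. Treating staff know which device is in use, and no concurrent arm would reveal a shift in goals.

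The window adds to the problem. Maintenance has no stated start or end. If it begins when goal is reached, the choice of goal also changes the denominator, and a patient who never reaches goal may have no maintenance period at all. The study period is not defined either, and on a plain reading it would take in induction and rewarming.

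The stake is the interpretation of the one comparison in the plan that has a numerical margin, in a group small enough that each patient contributes one fifteenth of the mean.

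**Working it through.** **1. The plan's own figure.** Inputs from Statistical analysis: 60% (standard), 85% (device), margin 15 points, alpha 0.05, power 80%. Treating time at goal as a yes/no proportion per patient, with one-sided alpha 0.05:

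n = (1.645 + 0.842)² × (0.60×0.40 + 0.85×0.15) / (0.25 + 0.15)² = 6.18 × 0.3675 / 0.16 = 14.2, rounded up to 15 per group.

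This matches the stated 15 (one-sided 0.025 gives 19). The goal temperature is not an input, so fixing the scoring rule does not alter the planned size. It alters what is scored.

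**2. Scoring model.** The documents give no temperature mean or SD, so these are assumptions. With T ~ Normal(m, s), the score against goal g is P(g−1 < T < g+1) = Φ((g+1−m)/s) − Φ((g−1−m)/s). The effect on the group mean is the change in score divided by 15, per patient.

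**3. Error from using 33°C for everyone.** Patient intended for 35°C and held at m = 35°C:

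| s (°C) | Score at 35°C | Score at 33°C | Loss on mean of 15, three such patients |
|---|---|---|---|
| 0.3 | 99.9% | 0.0% | 20.0 points |
| 0.5 | 95.4% | 2.3% | 18.6 points |
| 0.8 | 78.9% | 10.6% | 13.7 points |

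For s = 0.5: (95.4 − 2.3) × 3/15 = 18.6.

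**4. Effect of rescoring from 33 to 35°C.** Patient ordered to 33°C, s = 0.4°C, whole period rescored:

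| m (°C) | Score at 33°C | Score at 35°C | Gain | On mean of 15, one patient | Three patients |
|---|---|---|---|---|---|
| 34.0 | 50.0% | 50.0% | 0 | 0 | 0 |
| 34.2 | 30.9% | 69.1% | 38.3 | 2.6 | 7.7 |
| 34.6 | 6.7% | 93.3% | 86.6 | 5.8 | 17.3 |

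For m = 34.6: Φ(−1.5) = 0.067 at 33°C; Φ(3.5) − Φ(−1.5) = 0.933 at 35°C; 86.6/15 = 5.8; 5.8 is rounded from 5.77, and 5.77 × 3 = 17.3.

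**5. Change partway through.** If the goal in force is used and the change comes at mid-period, only the second half is credited to the new goal. At m = 34.6 the gain is 86.6/2 = 43.3 points, which is 2.9 on the mean for one patient and 8.7 for three.

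**6. Against the margin.** The upper end for three patients (17.3) slightly exceeds 15 points; the other cases in steps 4 and 5 fall below it. The plan's illustration sits (85 − 60) + 15 = 40 points above the non-inferiority bound, so a shift of this size does not by itself reverse a conclusion there.

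**The case against.** A reader might infer that a failing device can be turned into a success by relaxing the goal, that the bias necessarily favours the device, and that a few reset goals would decide the non-inferiority result. The documents do not support this.

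- The margin appears only beside the 33°C definition. Under that definition, moving a patient to a higher goal lowers the device's score.
- No section describes re-targeting. The 32 to 36°C range describes differences between centers, not changes within a patient. The sentence "Fluid and other management is left at the discretion of the attending physician" stands under Other treatments, after standard brain-injury care, and does not concern the cooling goal.
- Controls may have been re-targeted too, so the direction of any bias depends on how they are scored, which the plan does not say.
- The largest gain is one assumed case; the gain is zero at a mean of 34.0°C and roughly half for a mid-period change. No standard error or true difference was examined, so a reversed result has not been shown.
- The endpoint is secondary, and the final decision rule in Statistical analysis is written for the primary endpoint.
- The case report forms are not in the documents and may contain a goal field.

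All of these stand, and they limit the point. They do not remove the conflict over goal and window, or the absence of the prescribed goal from the protocol's own lists. Adopting 33°C throughout would settle the arithmetic, but it would mis-score patients treated to another goal by intent.

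**Conclusion.** The point holds as a conflict in the endpoint definition together with a recording gap. The two sections must be reconciled on goal and window, and the goal must be on record for either the intended or the in-force version to be scored reproducibly. Re-targeting is something the plan neither excludes nor would detect; it is not something the plan provides for.

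On the assumed temperatures, the choice of scoring goal moves the device mean by 0 to 5.8 points per affected patient in the rescoring case, and by 4.6 to 6.7 points per patient (13.7/3 to 20.0/3) where a patient intended for 35°C is scored against 33°C. With three affected patients, that ranges from nothing to about the size of the 15-point margin. These are illustrations: the normal model, the means, the SDs and the number of patients affected are all assumptions. They show that the ambiguity can be large relative to the margin, not that the conclusion would change.

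**What to change.** - Reconcile Secondary outcomes and Statistical analysis so that both use one definition of the goal and one time window, with a stated start and end that also covers patients who never reach goal.
- Record each patient's prescribed goal in °C, with clock time, before device cooling starts, and every later change with its time and reason.
- Score percent time against the original prescribed goal. Repeat against the goal in force as a sensitivity analysis, and report the number of patients re-targeted. The recorded reason should not determine the score, since that would bring back judgement by staff who know the device is in use.
- Apply the same rule to historical controls, using the charted order. Do not assign a goal afterwards.

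This concerns recording and scoring only; the choice of goal stays with the clinician. The planned 15 patients are unaffected. The cost is a few fields on the case report form, if they are not already there, and a short addition to the analysis text. The device percentage may come out slightly lower, and controls without a charted goal cannot be used for this endpoint, which may make it harder to find 15.

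### The arrhythmia and aspiration pneumonia outcomes do not require onset or worsening after device placement, and the baseline record only partly separates prior conditions

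*Combined protocol and SAP*

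**What the plan says.** The two definitions stand in the list of adverse events under Secondary outcomes:

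- "Cardiac arrhythmias - recording of atrial or ventricular arrhythmias during course of treatment".
- "Aspiration pneumonia - demonstration by chest X-ray of evidence of aspiration pneumonia, as diagnosed by treating physician, within 24 hours of cessation of device use".

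The first is anchored to treatment in general, the second to removal of the device. Neither is anchored to placement.

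The baseline items that bear on these events are under Screening on Day 1:

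- "Previous medical history and co-morbidities".
- A physical examination that covers "general appearance, heart, lungs, abdomen and extremities examinations".
- Concomitant medications.
- An electrocardiogram, coded "ECG (normal/STEMI/LBBB/other").
- "Blood gas and FiO₂ (pO₂, pCO₂, BE, pH, lactate").
- Among the pre-hospital data, "location patient intubated (on scene/in ambulance/in emergency department").

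No chest film is listed at screening. Exclusion criteria remove only patients whose prior conduction disorder is severe and needs pacing, so other prior arrhythmias may enrol. Data collection states that the time of ECD placement is recorded, and it describes the listed events as possible side effects. Study design compares outcomes with historical controls, without randomization.

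**The concern.** The study's stated aim includes the safety of the device. For that purpose the useful count is of events that arose or got worse once the device was in place. As written, a patient who arrives in atrial fibrillation and stays in it meets the arrhythmia outcome. A patient who aspirated before intubation can meet the other outcome if the film near device removal still shows it and the treating physician still diagnoses aspiration pneumonia. The intubation item itself allows for patients intubated on scene or in the ambulance.

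The protocol does guard against this elsewhere. Previous swallowing disorders are an exclusion, and dysphagia and odynophagia must last more than 24 hours after device use. Arrhythmia and aspiration pneumonia have no comparable safeguard.

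With 15 patients, one or two such cases visibly change a reported rate. Statistical analysis also speaks of margins for safety as well as efficacy. It gives no safety margin, so it is unclear whether these rates bear on a formal conclusion.

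**Working it through.** **1. Definitions against the placement time.** The placement time is recorded, but neither definition uses it. The protocol text describes no onset time, no relatedness assessment and no adjudication for these events.

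**2. What the baseline record can separate.**

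- *Arrhythmia:* history, concomitant medications and heart examination can identify a known, long-standing rhythm disorder. The ECG item cannot: a rhythm disorder with neither STEMI nor LBBB falls under other, together with every other abnormality. An arrhythmia provoked by the injury would not be in the history, and history from unconscious patients may be incomplete. Separation is partial.
- *Aspiration pneumonia:* lung examination, blood gas with FiO₂ and place of intubation are relevant but not specific. The outcome is read from a chest film, and no pre-placement film finding is listed to set beside it. Separation is weaker.

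**3. Size in the device group.** The documents give no event rate to reproduce. The denominator is 15, which Statistical analysis derives from percent of time at goal temperature, not from adverse events. Treating that percentage as a proportion, with 60% and 85%, a margin of 15 points, one-sided alpha 0.05 and 80% power:

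n = (1.645 + 0.842)² × (0.60×0.40 + 0.85×0.15) / (0.25 + 0.15)² = 6.18 × 0.3675 / 0.16 = 14.2, rounded up to 15.

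Each patient counted for a pre-placement condition adds 1/15 = 6.7 points; two add 2/15 = 13.3; three add 3/15 = 20.0. The range 0 to 3 is an assumption.

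**4. Size with an assumed prevalence.** Let *b* be the proportion counted because of a pre-placement condition, and *i* the risk of a new event in the rest. For aspiration pneumonia, *b* covers only cases still visible and still so diagnosed in the window.

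- With no new events, the expected count is 15*b* and the chance of at least one is 1 − (1 − *b*)¹⁵. For *b* = 10% this is 1.5 patients and 79%; for *b* = 40% it is 6.0 patients and over 99%.
- The counted rate is R = *b* + (1 − *b*)*i*. For *b* = 20% and *i* = 10%, R = 0.20 + 0.80×0.10 = 28%, or 4.2 of 15 patients. Of these, 15×0.80×0.10 = 1.2 are new.

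**5. Direction against historical controls.** Apply R to both groups, again with assumed values:

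- Same new-event risk (10%), device *b* = 20%, control *b* = 10%: 28% against 0.10 + 0.90×0.10 = 19%. The device looks 9 points worse with no true difference. Exchange the two values of *b* and it looks 9 points better.
- Device *b* = 10%, *i* = 20%: 0.10 + 0.90×0.20 = 28%. Control *b* = 20%, *i* = 10%: 28%. A doubled new-event risk disappears.
- Equal *b* = 20%, *i* = 20% against 10%: 36% against 28%. A true 10-point difference shrinks to 8.

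The sign therefore depends on *b* in the controls and on how their events were found. The protocol describes neither.

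**The case against.** Two stronger readings are tempting, and the documents support neither.

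- *A reader might infer that the baseline record cannot separate prior conditions at all.* It can in part. History, medications, heart and lung examination and the recorded placement time are all there, and long-standing atrial fibrillation is just what a medical history should capture. The gap is the coarse ECG code and the missing film finding.
- *A reader might infer that effects of the injury are counted as device harm.* The protocol lists these as adverse events and safety outcomes and calls them possible side effects, but does not attribute them to the device. Controls may carry injury-related events too, and an all-cause count in both groups need not disfavour the device.

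Other points also have force. Aspiration before intubation, or a residual shadow, is not enough by itself; a physician must diagnose aspiration pneumonia. The case report form is not in the documents, so it may hold onset or relatedness fields that cannot be seen here. The 6.7 points is the weight of any one patient among 15, not evidence that such patients will occur, and no stated threshold is shown to be crossed. Finally, counting every event is a defensible conservative choice in a small safety study, while a new-or-worsened filter brings in unblinded judgement and could hide real events.

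That last point argues for keeping the all-cause count, not for reporting it alone. It remains that the definitions set no onset condition and that the listed baseline items do not fill the gap.

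**Conclusion.** The point holds as a gap in definition and baseline recording for two secondary safety outcomes. Conditions present before ECD placement can enter the reported rates, at 6.7 percentage points per patient. The number of such patients is not in the documents; 0 to 20 points rests on an assumed 0 to 3 of 15, and the prevalences and event risks in the working are likewise assumptions. The direction of any bias against historical controls is unknown, because their baseline prevalence and ascertainment are not described. The ambiguity runs both ways: without baseline status, a true device event could also be dismissed as part of the injury. The primary outcome, time to initiation, is not affected. The change is worth making because without it these safety rates cannot be read cleanly.

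**What to change.** - Report arrhythmia and aspiration pneumonia each in two ways: all-cause, as now defined, and new or worsened after the recorded ECD placement time.
- Record the onset of each event relative to placement.
- Add rhythm to the baseline ECG item: sinus, atrial arrhythmia, ventricular arrhythmia or paced.
- Add a baseline item filled from routine imaging only: infiltrate or aspiration before ECD placement, yes / no / no film.
- List pre-existing conditions separately from events.
- Compare with historical controls on the new-or-worsened count only where their records allow the same rule; otherwise compare on the all-cause count, and say so.

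The cost is a short wording amendment and a small change to the case report form. No extra test or patient is needed. The downside is some unblinded judgement in calling an event new or worsened; showing the all-cause count beside it keeps that judgement visible.

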After the first 24 hours from the admission of the patient to the hospital Simplified Acute Physiology Score (SAPS) III will be measured.

Daily during day 1-7 if ICU stay the following procedures and assessments will be performed and recorded in the CRFs:

- Sequential Organ Failure Assessment (SOFA) scores;
- GCS scores;
- Pupillary and corneal reflex check;
- Highest body temperature;
- Highest dose and type of vasopressor/inotropic medication;
- The need for pacing;
- Intracranial pressure monitor pressures will be recorded (if measured);
- Recording of a need for mechanical circulatory assistance;
- Mechanical ventilation (if necessary);
- Recording of daily net fluid balance;
- Recording of adverse events;

Daily from day 8 to ICU discharge or day 14 the following records will be made:

- Patient comatose (yes or no);
- Mechanical ventilation (yes or no);
- Renal replacement therapy (yes or no);
- Presence of pneumonia (aspiration/non-aspiration) and sepsis (yes or no)

CPC should be assessed and recorded daily with the last recording being either at discharge, or at the 30 day time point.

Daily from day 1 to day 14 “do not attempt resuscitation order” should be recorded in the CRFs.

Based on investigator’s discretion, the following procedures may be performed if a decision is being contemplated for withdrawal of patient care”:

- Results and time of SSEP, if performed (n20 present bilaterally/n20 present unilaterally/n20 absent);
- Results and time of EEG, if performed.

At ICU discharge or 30 days from admission the following procedures will be recorded if performed (only CPC and GCS are mandatory):

- EEG, MRI, CT (if performed)
- CPC and GCS;

- Esophagogastroduodenoscopy (if performed)

Throughout the entire study:

- Concomitant medications;
- Adverse events

Statistical analysis

Sample size for primary outcome is calculated with an assumption of time to initiate cooling being approximately 5 minutes, with standard deviation of 4 minutes for the esophageal cooling device, and 20 minutes, with standard deviation of 15 minutes, for alternative devices. A power of 80%, and alpha of 5%, yields a sample size of 14 patients (with an equivalent size of historical controls). Sample size for secondary outcome is calculated for a non-inferiority test against the

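### Pneumonia counts as a safety outcome only within 24 hours of device removal, so new cases on the protocol's own day 8–14 pneumonia item normally fall outside it

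*Combined protocol and SAP*

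**What the plan says.** The combined protocol and SAP lists ten adverse events as secondary safety outcomes; two are pneumonias. The lead-in to the definitions (Secondary outcomes) says that "the methods used to identify and diagnose each during the treatment and 30-day follow-up phases are as follows". The two pneumonia definitions then set a much shorter window:

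- For the aspiration type, the protocol asks for "demonstration by chest X-ray of evidence of aspiration pneumonia, as diagnosed by treating physician, within 24 hours of cessation of device use".
- The entry for the non-aspiration type carries the same limit and requires "demonstration by chest X-ray of evidence of pneumonia within 24 hours of cessation of device use", with the treating physician classifying it as non-aspiration.

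The schedule under Study assessments and procedures has three relevant parts:

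- Days 1–7: "Daily during day 1-7 if ICU stay the following procedures and assessments will be performed and recorded in the CRFs". The list includes "Recording of adverse events" but no item that names pneumonia.
- From day 8: "Daily from day 8 to ICU discharge or day 14 the following records will be made". This list contains "Presence of pneumonia (aspiration/non-aspiration) and sepsis (yes or no".
- The whole study: adverse events are listed again as a running record, and the Data collection section says the listed side effects are recorded throughout.

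The Data collection section asks for the time of device placement. No section lists the time of removal, and no chest X-ray is scheduled.

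**The concern.** The outcome definition and the pneumonia-specific data item cover different periods. The protocol collects pneumonia on days 8–14 but defines the outcome so that a new case in that period would normally not qualify. It also does not say how those entries are to be reported.

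Three further gaps make the window hard to apply:

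- The wording can be read as the 24 hours after removal only, as 24 hours either side of removal, or as any time up to 24 hours after removal. Pneumonia that arises earlier, with the device in place, counts only under the last reading. The arrhythmia definition states on-treatment coverage explicitly; the pneumonia definitions do not.
- The window is anchored on a time that the protocol does not list for recording.
- The Study design section plans a comparison with historical controls, for whom removal of this device has no defined meaning.

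Safety is a stated aim and the sample is 15 patients. A low pneumonia count that follows from a narrow window could be taken as reassurance about the device.

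**Working it through.** The plan states no pneumonia rate, event count or power that rests on this window, so there is no figure to reproduce. The check compares time intervals.

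**Inputs**
- Counting window, narrowest reading: from removal time T to T + 24 h (Secondary outcomes).
- Pneumonia item: days 8–14. If day d runs from 24(d − 1) to 24d hours after time zero, this is 168–336 h.
- Daily adverse-event record: days 1–7, that is 0–168 h, during ICU stay.
- T is not stated. Hourly temperatures run to 39 h, so T = 39 h serves as an assumed central value. The range examined is 24–168 h.

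**Overlap** = max(0, earlier of the two ends − later of the two starts)

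| T (h), assumed | Window (h) | Overlap with day 8–14 item (h) | Overlap with day 1–7 AE record (h) |
|---|---|---|---|
| 24 | 24–48 | 0 | 24 |
| 39 | 39–63 | 0 | 24 |
| 72 | 72–96 | 0 | 24 |
| 144 | 144–168 | 0 | 24 |
| 150 | 150–174 | 6 | 18 |
| 168 | 168–192 | 24 | 0 |

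At T = 39 h the window closes 168 − 63 = 105 h before the pneumonia item starts. The threshold is 168 − 24 = 144 h. If days are calendar days, day 8 can start up to 24 h sooner and the threshold falls to as little as 120 h.

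The day 8–14 item records presence, not onset. A tick on day 8 could be an older, in-window pneumonia that has persisted. The mismatch therefore concerns new cases, and the item alone cannot tell the two apart.

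**Weight of one patient.** 1/15 = 6.7 percentage points on the reported proportion. Even 0/15 has an exact two-sided 95% upper limit of 1 − 0.025^(1/15) = 0.22.

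**Illustration only; none of these inputs is in the documents.** Assume a constant hazard over 336 h and a 14-day risk R of 20–50%, with T of 39–72 h. Then h = −ln(1 − R)/336.
- Placement to 24 h after removal: share captured = [1 − exp(−h(T + 24))]/R. For R = 0.20 and T = 39, 0.041/0.20 = 0.20. For R = 0.50 and T = 72, 0.180/0.50 = 0.36.
- The 24 h after removal only: share captured = [exp(−hT) − exp(−h(T + 24))]/R, about 0.08 to 0.09 over the same range.

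The two readings differ by a factor of roughly 2.5 to 4 under identical assumptions, so the wording needs settling. The shares do not estimate what this trial would miss.

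**The case against.** The strongest reply is that the protocol does schedule a record covering the counting window. For removal at 24–144 h, all 24 hours lie inside the daily adverse-event record for days 1–7, and the study-wide record covers patients who have left the ICU. Both pneumonias are named adverse events, so both belong there. This stands. A reader might infer that pneumonia data are collected only on days 8–14, or that the outcome and its data collection hardly meet. The documents do not support that: what is missing on days 1–7 is a pneumonia-specific prompt, not a scheduled record.

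A reader might also infer that later pneumonias disappear from safety reporting. They fall outside the two defined outcomes, but the list of adverse events is open-ended, and a pneumonia that prolongs hospitalization meets the SAE definition. Nothing says such events are discarded. The gap is that no rule says where they are reported.

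A window tied to device use is also a legitimate way to support attribution. Other events have their own windows, such as reflux within 3 days of recovery, and the lead-in need not mean that every event is counted for 30 days. This justifies keeping a device-period count. It does not explain why pneumonia is collected on days 8–14 without a stated use, and it does not settle whether on-device cases count.

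**Conclusion.** The point holds as a mismatch between definition and schedule. New pneumonias on the day 8–14 item fall outside the outcome unless the device is removed after 144 h (about 120 h at the least, if days are calendar days). Whether pneumonia during device use counts is unclear, and in-window cases rely on adverse-event reporting that does not ask about pneumonia. Two of the ten named safety outcomes are affected.

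Exclusion of later cases follows from the definition. Loss of in-window cases is a risk that the documents do not demonstrate. A reader might want to attach a percentage to the undercount, but the protocol gives no device duration, pneumonia rate or onset timing, so any such percentage would come from the assumptions alone. The change is worth making because it is cheap and uses data largely already collected.

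**What to change.** 1. Define the pneumonia safety outcome as physician-diagnosed pneumonia with X-ray evidence, aspiration and non-aspiration separately, from device placement through day 14 (or day 30).
2. Report the subset from placement to 24 hours after removal as the device-period count. This keeps the attribution question visible and settles how on-device cases are treated.
3. Add the existing yes/no item to the day 1–7 list. Because a tick alone does not establish X-ray evidence or onset, record the date of the X-ray on which the diagnosis rests.
4. Record the time of device removal alongside the time of placement.
5. Compare with historical controls only over a window for which their records date the pneumonia. The Statistical analysis section describes them only by available endoscopy, so such dates may not exist; in that case, report the pneumonia count for the device group without comparison.

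The cost is revised definition wording, a few CRF lines and a less favourable reported pneumonia rate. After ICU discharge, and on days 15–30 if the longer window is chosen, capture would rest on the study-wide adverse-event record. Sample size and treatment are unaffected.
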